10.5.1 Adverse Events and Complications

All subject questionnaire data, complications, and adverse events will be tabulated and summarized.

10.5.2 Glasgow Benefit Inventory (GBI) Questionnaire

The effectiveness parameter evaluated will be the mean composite score for the GBI administered post-treatment at the 1-4 month post-operative follow-up visit. The GBI will be administered at each post-operative visit. It is believed that the positive effect of the surgery will have manifested itself in GBI score by the 2nd follow-up visit. A 95% t confidence interval will be used to estimate the mean score.

Scoring the GBI will follow the standard protocol (**Appendix A**). Positive scores indicate improvement from pre-treatment; negative scores indicate deterioration.

As part of the GBI protocol, it is expected that researchers may need to change the format or appearance of items to suit their purposes.

10.5.3. Lac-Q Questionnaire (Appendix B)

This study does not aim to assess the effectiveness of the DCR procedure, which is a well-established surgical procedure for the treatment of epiphora secondary to nasolacrimal duct obstruction. Furthermore, the study does not aim to assess the effectiveness of using a silicone lacrimal stent as part of a lacrimal procedure. Rather, the primary goal of this study is to assess patient tolerance of the Slit Stent II, which introduces novel cuts into the traditional stent that allow for intraluminal tear drainage. The secondary goal of the study is to confirm that the Slit Stent II functions like any other silicone lacrimal stent as an adjunct to a lacrimal procedure. The effectiveness of the procedure in relieving the tearing symptoms and associated social isolation will be assessed at the pre-op visit and at each post-op visit. Scoring will follow the standard protocol (**Appendix B**). The Lac-Q questionnaire will always be given first among the questionnaires.

10.5.4 Other Outcome Measures

Other outcome measures, such as slit lamp biomicroscopy, will be reported in data line listings.

10.6 Dropouts/Lost-to-Follow-up

Subjects may drop out at any time during the study. All treated subjects/eyes will be included in the safety analysis.

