7.0 SUBJECT POPULATION

This is a single center study that will be conducted at the University of Michigan (Ann Arbor, Michigan). Fifty (50) subjects will be enrolled and treated with either the experimental Slit Stent II (25 patients) or the control stent BIKA for DCR (25 patients). Patients who are currently scheduled to undergo a DCR (dacryocystorhinostomy) as per standard of care will be offered participation in the study. Patients who elect to participate in the study will be consented and then randomized to the treatment or control arm.

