8.2 Examination Schedule

The following examination schedule will be followed from screening through the postoperative visits:

- Screening (Day -60 to Day 0 Preoperatively)
- Device implantation operation
- Phone call Assessment at 1 day post op
- Phone call Assessment at 45 days post op (+/- 15 days)
- Day 5-14 postoperatively
- Day 30-120 postoperatively (with stent removal)
- 5-7 month final post-operative exam

The screening visit should be completed anytime within the 60 days prior to the scheduled surgery. Unscheduled visits may be completed at the investigator's discretion or as medically necessary before or after the implant surgery.

All final exam procedures will be completed at the second post-operative study visit.

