10.0 DATA ANALYSIS AND STATISTICAL CONSIDERATIONS

A detailed statistical analysis plan (SAP) will be developed for analysis of all data for this study. Required analyses and target endpoints that will be included in this SAP are summarized below. The methods by which each of these analyses is performed will be included in the SAP. The required analyses and target endpoints for the Slit Stent II include, but are not limited to, those listed below. If there are any discrepancies between the statistical analyses described in the SAP versus this protocol, the SAP will prevail. Tabulation of summary statistics, graphical presentations, and statistical analyses will be performed using SAS® and/or R software. All subjects who are enrolled in this study will be included in the safety analysis. All testing and confidence intervals will use a two-sided significance level of 5%.

Specific analyses for the six listed objectives are very similar to one another. Data will be summarized by treatment group (Slit Stent II or BIKA for DCR): counts and percentages for categorical variables, means and standard deviations for continuous variables. Additionally, 95% confidence intervals will be provided for each treatment group and for the difference between treatment groups. The confidence intervals for differences are keys to exhibiting the similarity between the Slit Stent II and the existing BIKA stent.

As this is a randomized experiment, control for pre-treatment variables is not necessary. However, a sensitivity analysis controlling for the baseline measurement of the outcome variable will be conducted. For example, post-surgery Lac-Q will be regressed on treatment and pre-surgery Lac-Q. If pre- and post-surgery measures are highly correlated, the confidence interval for the treatment effect will be narrower (more precise). If measurements are made at multiple post-surgery time-points, (generalized) linear mixed models will be used to estimate an overall (fixed) treatment effect while accounting for any correlation between measurements on the same person (random intercept).

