10.5 Outcome Criteria

Complications and adverse events are the primary safety outcomes to be evaluated. All complications and adverse events and their rates of occurrence will be reported. Changes in the subject's symptoms (tearing, irritation) and quality of life as measured by the GBI are the primary effectiveness outcomes.

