11.3 Complications and Adverse Events

Adverse events will be recorded from the time of surgical implantation of the device until the final visit. Ophthalmic complications or adverse events that are observed by the investigator or

reported by the subject should be recorded on the CRFs. For all adverse events and complications, a description of the event, date first observed, any action taken, and ultimate outcome will be recorded.

For all adverse effects, sufficient information will be pursued and/or obtained so as to permit 1) an adequate determination of the outcome of the effect (i.e., whether the effect should be classified as a *serious adverse effect*) and; 2) an assessment of the causal relationship between the adverse effect and the investigational device or, if applicable, the other study treatment or diagnostic product(s).

Adverse effects felt to be associated with the investigational device or, if applicable, other study treatment or diagnostic product(s) will be followed until the effect (or its sequelae) or the abnormal test finding resolves or stabilizes at a level acceptable to the Sponsor Investigator.

All adverse events will be reported to the IRB according to local policies and to the FDA according the regulations found in 21 CFR 812.150.

Complications and adverse events that occur in the study can be caused by the Slit Stent II, by the standard stent, or by the surgical DCR procedure, and are identical to the risks already associated with DCR surgery and BIKa for DCR stent placement (see Section 3.1). Potential complications include, but are not limited to the following:

- bleeding from nose
- infection
- irritation or discomfort
- conjunctival or nasal pruritus
- nasal mucosa or caruncular irritation
- reversible shrinkage of the palpebral fissure
- exteriorization or loss of the stent tubing
- punctal/canalicular injury
- canaliculitis
- Synechia of the nasal mucosa
- Induced mucocele
- Device dislocation into the oropharynx
- Corneal abrasion
- loss of the device (falling out or inadvertently swallowing)
- Conjunctival abrasion
- Secondary surgical interventions related to the Slit Stent II device (surgical repositioning, removal, or replacement)
- False passages
- Separation of the silicone from the steel guide

- Breakage of the stent during insertion or postoperatively
- Strictureotomy

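### The safety set is all enrolled subjects in section 10.0 but all treated subjects in 10.6; if any enrolled subject is never implanted, the 10.0 rule lowers the primary safety rates

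*Combined protocol and SAP*

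**What the plan says.** Two sentences describe who enters the safety analysis:

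- Section 10.0: "All subjects who are enrolled in this study will be included in the safety analysis".
- Section 10.6: "All treated subjects/eyes will be included in the safety analysis".

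Section 10.5 makes this the principal safety question: "Complications and adverse events are the primary safety outcomes to be evaluated". It adds "All complications and adverse events and their rates of occurrence will be reported", but names no denominator for those rates.

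On collection, section 11.3 says "Adverse events will be recorded from the time of surgical implantation of the device until the final visit". The flow chart in Appendix D agrees: its first adverse-event mark is in the surgery column, with none at screening.

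On the order of events, section 7.0 says "Patients who elect to participate in the study will be consented and then randomized to the treatment or control arm", and section 8.2 says "The screening visit should be completed anytime within the 60 days prior to the scheduled surgery". The precedence rule in section 10.0 ranks a separate SAP above the protocol. It does not rank 10.0 against 10.6.

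**The concern.** A rate needs one denominator, and the plan offers two for its primary safety outcome. They differ by exactly those subjects who are enrolled but never receive a stent. The recording rule gives these subjects no opportunity to have an event counted, so they can only pull the rate down.

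The plan leaves room for them. Section 9.3 allows reassessment of eligibility on the day of surgery, section 9.9 allows withdrawal at any time, and the accountability table in section 10.2 defines its total by enrolment and not by implantation.

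At stake is a modest understatement of complication rates for a modified device. If a similar number in each arm goes untreated, the between-arm difference also shrinks, and section 10.0 relies on the intervals for differences to show that the two stents are alike. Leaving the choice open also means that the denominator could be picked after the data are seen.

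**Working it through.** **Inputs from the documents.** 25 subjects planned per arm (7.0, 10.1); the two safety-set sentences (10.0, 10.6); recording from implantation (11.3); maximum half width of a 95% Wilson interval for one proportion at n = 25, given as 0.18 (10.1).

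**Assumptions.** The documents give neither an expected event rate nor a number enrolled but untreated. I take 5 subjects with an event in an arm, and let u be the number untreated in that arm.

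**The plan's own figure.** The Wilson half width is z·√[p(1−p)/n + z²/(4n²)] / (1 + z²/n), with z = 1.96. The largest value over 0 to 25 events occurs at 12 or 13 of 25. With p = 0.48: 1.96 × √(0.009984 + 0.001537) / 1.1537 = 0.182. The stated 0.18 reproduces.

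**Effect of the denominator.** With x subjects having an event, the treated-set rate is x / n_treated and the all-enrolled rate is x / n_enrolled. Hence

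rate(enrolled) = rate(treated) × n_treated / n_enrolled.

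With 25 enrolled in an arm and x = 5:

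| u | Factor | Rate on treated | Rate on enrolled |
|---|---|---|---|
| 0 | 25/25 = 1.00 | 5/25 = 20.0% | 20.0% |
| 1 | 24/25 = 0.96 | 5/24 = 20.8% | 20.0% |
| 2 | 23/25 = 0.92 | 5/23 = 21.7% | 20.0% |
| 3 | 22/25 = 0.88 | 5/22 = 22.7% | 20.0% |
| 5 | 20/25 = 0.80 | 5/20 = 25.0% | 20.0% |

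Each untreated subject lowers the rate by 1/25 = 4% in relative terms.

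If instead 25 are treated and u more are enrolled, a true 20.0% is reported as 5/26 = 19.2% (u = 1), 5/27 = 18.5% (u = 2) or 5/30 = 16.7% (u = 5).

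**No events observed.** The exact two-sided 95% upper limit is 1 − 0.025^(1/n). That is 13.7% on 25 enrolled and 14.8% on 23 treated.

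**Difference between arms.** With 8 against 4 subjects having an event and u = 2 in each arm: (8 − 4)/23 = 17.4 points on treated, and (8 − 4)/25 = 16.0 points on enrolled.

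**Against the plan's precision.** At u = 2 the shift is 21.7 − 20.0 = 1.7 points, compared with a half width of about 18 points.

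**The case against.** The best reply is that the two sentences do not conflict. Treated subjects are a subset of enrolled ones, and 10.6 sits under a heading about dropouts, so it may only mean that treated subjects who later leave are kept. As statements of inclusion, that is right. It does not settle the denominator: 10.0 taken literally still brings in untreated subjects, and no section says otherwise.

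The plan also expects the two groups to coincide. Section 7.0 foresees 50 subjects both enrolled and treated, section 10.3 keeps ineligible screened subjects out of the analysis, and section 11.1 places consent before enrolment, so consent alone does not make a subject enrolled. This stands. The effect is conditional, and it may be zero.

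Section 10.0 also defers methods to a detailed SAP that would prevail. An analysis set could be fixed there, but the documents contain no separate SAP that does so.

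Two stronger readings are tempting, and the documents support neither:

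- *That subjects are randomised as much as 60 days before surgery.* Sixty days is the screening window, which runs up to the day of operation. Section 7.0 gives the order of consent and randomisation but no date. Sections 9.0 and 9.3 describe a list held by the coordinator, with the stent supplied on the day, so assignment close to surgery fits the text equally well.
- *That the two arms would be biased by different amounts.* Section 9.0 masks surgical, recruitment and scheduling staff until the day of surgery, and section 9.3 keeps the stent type from the patient. There is no evident route for cancellations to depend on arm, so an imbalance would arise mainly by chance.

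**Conclusion.** The concern holds in a limited form. The plan states two safety sets and names no denominator. Combined with the recording rule, the wider set lowers the primary safety rates whenever an enrolled subject goes unimplanted. The direction is fixed; the size is not known. It is about 4% relative per untreated subject among 25, so 1.7 points at two untreated under the assumed 5 events, and nothing if all are implanted.

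A reader might infer that the reported complication rates will certainly be diluted. The documents do not show this, because they give no number of untreated subjects. A shift of this order would be hard to see beside the width of the intervals, and the documents state no safety threshold or powered safety test that depends on it. This is a correction worth making, not a threat to the trial's conclusions.

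**What to change.** In section 10.0, replace the enrolled set with the treated set already named in 10.6, and define it identically in both places, for example:

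*The safety set comprises all subjects in whom placement of a study stent was performed or attempted, grouped by the stent received or, if none was placed, by the stent attempted. It is the denominator for all adverse event and complication rates.*

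Refer to that set in section 10.5. Including attempted placements keeps in events that section 11.3 lists and that can occur without a completed implantation, such as breakage during insertion or false passages. The clause for subjects with no stent placed is needed because they cannot be classified by stent received.

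The cost is about one sentence plus a cross-reference, best settled before unblinded data are seen. The downside is that enrolled but untreated subjects would be reported only in the accountability table, and the safety denominators may be slightly smaller. Sample size and power do not change.

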10.7 Missing data

The amount of missing data will be minimized by careful recordkeeping and diligent follow-up. Modern imputation methods will be used to complete specified analyses. To assess the impact of missing data, sensitivity analyses will be conducted. The primary endpoints will be assessed in worst case and best case scenarios. The number of missing data points in this type of study is anticipated to be small. The sensitivity analyses will likely yield results similar to the main analysis.

The study results will be submitted for publication or presentation regardless of the study outcome following the conclusion or termination of the trial.

11.0 ETHICAL AND REGULATORY CONSIDERATIONS

This study will be conducted in accordance with FDA's Good Clinical Practice regulations.

11.1 Informed Consent

In accordance with the provision of 21 CFR Part 50, each subject will provide written informed consent for participation in this study prior to enrollment into the study.

The study will be explained to the prospective subject by the investigator or his designee. The nature of the experimental product will be explained together with potential hazards of the surgical procedure, including any possible adverse reactions. The subject will be informed that he/she is free to terminate participation in the study for any reason. One copy of the signed consent form will be retained in the medical record, and one copy will be given to the subject.

11.2 Institutional Review Board

This protocol and the ICF will be approved initially and reviewed annually by the University of Michigan Institutional Review Board (IRB). Progress reports will be submitted at the completion of the study or at least once yearly, whichever comes first, to the IRB. Serious adverse events will be reported to the IRB and the FDA in accordance with IRB Reporting Criteria Guidelines and applicable FDA regulations for serious adverse events.

11.3 Complications and Adverse Events

Adverse events will be recorded from the time of surgical implantation of the device until the final visit. Ophthalmic complications or adverse events that are observed by the investigator or

reported by the subject should be recorded on the CRFs. For all adverse events and complications, a description of the event, date first observed, any action taken, and ultimate outcome will be recorded.

For all adverse effects, sufficient information will be pursued and/or obtained so as to permit 1) an adequate determination of the outcome of the effect (i.e., whether the effect should be classified as a *serious adverse effect*) and; 2) an assessment of the causal relationship between the adverse effect and the investigational device or, if applicable, the other study treatment or diagnostic product(s).

Adverse effects felt to be associated with the investigational device or, if applicable, other study treatment or diagnostic product(s) will be followed until the effect (or its sequelae) or the abnormal test finding resolves or stabilizes at a level acceptable to the Sponsor Investigator.

All adverse events will be reported to the IRB according to local policies and to the FDA according the regulations found in 21 CFR 812.150.

Complications and adverse events that occur in the study can be caused by the Slit Stent II, by the standard stent, or by the surgical DCR procedure, and are identical to the risks already associated with DCR surgery and BIKa for DCR stent placement (see Section 3.1). Potential complications include, but are not limited to the following:

- bleeding from nose
- infection
- irritation or discomfort
- conjunctival or nasal pruritus
- nasal mucosa or caruncular irritation
- reversible shrinkage of the palpebral fissure
- exteriorization or loss of the stent tubing
- punctal/canalicular injury
- canaliculitis
- Synechia of the nasal mucosa
- Induced mucocele
- Device dislocation into the oropharynx
- Corneal abrasion
- loss of the device (falling out or inadvertently swallowing)
- Conjunctival abrasion
- Secondary surgical interventions related to the Slit Stent II device (surgical repositioning, removal, or replacement)
- False passages
- Separation of the silicone from the steel guide

- Breakage of the stent during insertion or postoperatively
- Strictureotomy

All ophthalmic adverse events should be recorded on the adverse event forms in the CRFs. Adverse device effects /events that are determined by the sponsor investigator to be vision-threatening should be considered to be reportable as described below.

Adverse events that occur in association with a device that is used in conjunction with the Slit Stent II will be reported separately.

Postoperative observations that, after sponsor investigator review, are determined to be part of the normal healing process that occurs after the nasolacrimal intubation procedure are not considered to be reportable events.

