- **Adverse events, complications, visual disturbances-** Visual disturbances are any unexpected, expected, or pre-existing sight related occurrences that are not captured in any of the examinations or measurements, such as nystagmus or diplopia.

Unexpected or new reports of visual disturbances related to the device or surgical procedure should be recorded on the complications/adverse event case report form.

In addition to the above procedures, **at the day 30-120 visit**, we will collect, examine (photo) and culture all stents after retrieval from the nose. Culturing will consist of placing the retrieved stent in a standard container and submitting it to microbiology for culture and sensitivities.

Removal of the stent entails cutting the holding suture in the nose with scissors under direct visualization, with the help of a nasal speculum if needed, cutting the stent itself with scissors once to linearize it, and then pulling the stent out either from the nose or from the puncta using forceps.

Upon stent removal, the surgeon will comment on whether stent removal was technically simple, moderate or difficult (binary). This will be recorded on the CRF.

At the Final Visit, month 5-7, the following procedures will be performed:

- **Documentation of interim medical, ocular, and medication histories** since previous visit. The ocular history should capture any changes in the study eye since the previous visit; and, any relevant changes to the fellow eye that are necessary to evaluate an adverse event or anomaly in the study eye. The medication history should capture any changes in prescribed medications or routinely taken non-prescription medication since the previous visit.
- **Lac-Q questionnaire (Appendix B)**
- **Glasgow Benefit Inventory Questionnaire (Appendix A).**
 - **The 2 questionnaires will always be given in the same order: 1) Lac-Q, 2) GBI.**
- **Corrected distance visual acuity** - Corrected visual acuity is measured in each eye by the ETDRS chart at 3 meters. If there is a 2-line or more reduction in visual acuity from the last corrected visual acuity, a repeat manifest refraction in - each eye will be performed.
- **External exam of the medial canthal area and the medial commissure**

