9.6 Safety Monitoring

Subjects will be observed closely to detect any adverse events or complications that may have occurred. On the day of treatment and at each follow-up visit, subjects should be asked a non-leading question, such as "How are your eyes?" to determine whether any complications or adverse events might have occurred since the last visit. The presence or absence of adverse

events or complications will be documented. All exam findings, work-up, management, and sequelae relevant to an AE will be recorded on the AE CRF.

Ophthalmic safety will be evaluated by slit lamp biomicroscopy of the operated eye. In the case of an adverse event or complication, these tests, and any others deemed necessary, may be repeated before the next scheduled visit at the investigator's discretion. Appropriate supportive and/or definitive therapy may be administered as required. Any complications or adverse events will be recorded in the medical record/CRF.

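### Symptom-free nasal signs count towards the primary safety outcome but are captured only passively; record them by prompt for every subject at stent removal

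*Combined protocol and SAP*

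**What the plan says.** Section 10.5 states "Complications and adverse events are the primary safety outcomes to be evaluated" and adds "All complications and adverse events and their rates of occurrence will be reported". Section 11.3 lists 20 potential complications, without claiming the list is complete; it includes nasal mucosal irritation and "Synechia of the nasal mucosa".

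The scheduled post-operative assessments (section 9.4, Appendix D) are histories, questionnaires, visual acuity, intraocular pressure, slit lamp, inspection of the stent at the medial commissure while it is in place, and an external examination. For the final visit, section 9.4 describes the external examination as covering the medial canthus and commissure. No row of the flow chart is a nasal examination.

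Section 9.6 says "Ophthalmic safety will be evaluated by slit lamp biomicroscopy of the operated eye" and offers "How are your eyes" as an example of the opening safety question. It names no counterpart for the nose.

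At removal, section 9.4 describes "cutting the holding suture in the nose with scissors under direct visualization, with the help of a nasal speculum if needed". The results it then asks for are the surgeon's grading of how easy removal was and, for the device, "we will collect, examine (photo) and culture all stents after retrieval from the nose". No finding on the nasal lining is requested.

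Two provisions work the other way. Section 9.4 requires complications that the investigator observes or the subject reports to go on the CRF. Section 9.6 requires their presence or absence to be documented on the day of treatment and at each follow-up visit.

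**The concern.** A complication rate needs a numerator of events found and a denominator of subjects in whom they could have been found. For events that subjects feel, spontaneous report supplies both reasonably well. For a sign that can only be seen, such as a synechia without symptoms, the denominator is the number of noses inspected, and the plan does not establish it. A blank entry could mean that the mucosa was inspected and was normal, or that nobody inspected it.

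This bears on the trial's argument because section 10.0 treats confidence intervals for between-arm differences as the main evidence that the two stents are similar. Under-detection that is equal in both arms shrinks a difference in rates towards zero, in the direction of that conclusion. The nose is also a relevant site: the stent passes into it, and the slits are meant to drain tears there (sections 1.2 and 2.3).

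**Working it through.** **1. Which listed complications depend on inspection?** Five of the 20 items in section 11.3 involve the nose or oropharynx.

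| Item | Route of capture under the plan |
|---|---|
| Nose bleeding | Subject can report it |
| Nasal pruritus (listed with conjunctival) | A symptom; inspection adds nothing |
| Dislocation into the oropharynx | Stent presence at the commissure is recorded at both visits with the stent in place |
| Nasal mucosal irritation | Reported if felt; otherwise only if noticed |
| Synechia of the nasal mucosa | Only if noticed, when without symptoms |

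Only the last two leave a gap, and only when they cause no symptoms.

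**2. The plan's own precision figure.** Section 10.1 gives 0.18 as the maximum half width of a 95% Wilson interval for one proportion with n = 25. The half width is z·√(p(1−p)/n + z²/(4n²)) / (1 + z²/n). With z = 1.96, p = 0.5 and n = 25 it is 0.182, so the figure reproduces. It assumes that all 25 subjects were assessed.

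**3. What a zero count supports.** With 0 events among m subjects actually inspected, the exact two-sided 95% upper limit is 1 − 0.025^(1/m). The plan does not fix m, so a range is shown.

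| m inspected of 25 | Upper limit |
|---|---|
| 25 | 13.7% (Wilson: 13.3%) |
| 20 | 16.8% |
| 15 | 21.8% |
| 10 | 30.8% |
| 0 | none |

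If m is unknown, the 13.7% cannot be claimed.

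**4. Illustrations on assumed values.** The documents give no nasal complication rate and no detection probability, so these figures show direction and scale only.

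- *Limit on the true rate after 0/25*, if a fraction s of cases comes to light: 13.7%/s. For s = 0.7, 0.5 and 0.3 this is about 20%, 27% and 46%.
- *Chance that an arm records no case*, with true rate p: (1 − p·s)^25. At p = 10% this is 0.07 for s = 1 and 0.53 for s = 0.25. At p = 20% it is 0.004 and 0.28.
- *Apparent difference* for true rates of 20% and 4% with equal detection in both arms: 16·s points, that is 11.2, 8.0 and 4.8 points for s = 0.7, 0.5 and 0.3.

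**The case against.** The strongest case is that the plan already captures nasal harm. Observed and reported complications must be recorded, with no restriction to the eye in section 9.4. The flow chart has a complications row at surgery, at both phone calls and at every post-operative visit. Both calls ask about swelling, pain and other adverse effects. A surgeon who sees a synechia while cutting the suture is obliged to record it. In a 50-subject study, relying on spontaneous and observed events rather than a checklist is a legitimate choice. This stands, and it rules out the stronger reading that nasal complications go uncounted or that noting them is optional. What it leaves open is that a duty to record what is seen is not a duty to look.

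It is also fair that no nasal item is an endpoint in its own right: section 11.3 calls them potential complications, and they enter through the general wording of section 10.5. Section 11.3 further excludes from reportable events any observation judged part of normal healing, so some symptom-free irritation may not count as a complication at all. The CRFs are not in the documents and may already carry a prompt.

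Two limits concern the remedy. The surgical team is masked only until the day of surgery (section 9.0), so the person completing the new items will normally know the stent; prompted recording makes looking uniform but leaves judgement open to bias. And 25 per arm is too few for a reliable comparison even with full detection: for assumed rates of 20% and 4%, Fisher's exact test at the two-sided 5% level has about 23% power. The gain is an interpretable rate in each arm, not a test between them.

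**Conclusion.** The point holds in a narrow form. Nasal synechia and mucosal irritation fall within the primary safety outcome, no scheduled examination inspects the nose, and the one step at which it is viewed asks for no nasal finding. Symptom-free signs are therefore captured passively, and a recorded zero for them does not bound the rate. The 13.7% upper limit for 0/25 is valid only if all 25 were looked at.

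A reader might infer that all five nasal or oropharyngeal items are missed, or that the plan can be shown to understate nasal harm by a given amount. The documents support neither. Three of the five items are reportable by the subject or covered by the stent inspection. The detection fractions of 70%, 50% and 30% and the 20% versus 4% rates are illustrations, not estimates. Differential recording by arm is possible because the surgeon is unmasked, but nothing in the documents shows that it will occur.

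This is a low-cost improvement in ascertainment, not an error of arithmetic or a contradiction in the plan.

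**What to change.** Add to section 9.4 and to the day 30-120 CRF: *At stent removal, whether planned or early, while the nose is viewed to cut the holding suture, record for every subject in both arms whether nasal synechia and nasal mucosal irritation are each present, absent or not visible.*

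Add to section 10.5.1: *These findings will be tabulated by arm, with the number of subjects assessed as the denominator and a 95% confidence interval for each proportion.*

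The *not visible* option matters because a view good enough to cut a suture may not show the whole cavity; those subjects leave the denominator rather than count as negative.

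The cost is two items on a form already completed at that visit, with no new visit, procedure, staff or change in sample size. The downsides should be stated in the plan: observed nasal rates will rise in both arms, the assessor remains unmasked, and changes after removal, including any present at the month 5-7 visit, are not captured.
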